**Phase 1 Study: Detection of Brown Adipose Tissue in Normal  
Volunteers Using a 3 Tesla (3T) Magnetic Resonance Imaging System  
and Hyperpolarized (HP) Xenon Gas**

**NCT number** NCT02220426  
**Document Date** 10/09/2014

**SPECIFIC AIMS:** In spite of the many efforts to raise awareness on the health complications of obesity, our obesity epidemic keeps growing, adding an immense cost to our health care system. At a fundamental level obesity is the result of an imbalance between energy intake and energy expenditure. The latter is very difficult to quantify and recent work suggests that in humans it is partially modulated by the activity of Brown Adipose Tissue (BAT). BAT is a tissue with the unique capacity to regulate energy expenditure by a process called thermogenesis during which this tissue burns fat to produce heat. By preventing excessive accumulation of triglyceride in non-adipose tissues such as muscle and liver, this tissue also helps to protect against insulin resistance and type 2 diabetes.

As ways to harness this tissue to address obesity and diabetes are being investigated, its non invasive detection in humans remains an unmet need. The current gold standard for the detection of BAT activity is FDG-PET. Unfortunately this technique has obvious limitations: 1) It cannot be used for longitudinal studies in healthy subjects due to concerns over radiation exposure, 2) It is not reproducible, and 3) It fails in detecting BAT in the target population, i.e. in overweight and obese subjects. Other imaging modalities like MRI and CT have been tried, but aside from lacking specificity and their inability to detect BAT activity, they all share the same insensitivity to the lipid rich BAT present in overweight and obese subjects.

The goal of the proposed application is to provide a non-invasive imaging tool that is suitable to detect mass and metabolic activity of BAT in both lean and obese human subjects. Our group was the first to demonstrate the use of hyperpolarized xenon gas MRI to specifically and directly detect BAT mass and thermogenic activity in lean and obese mouse phenotypes, with unprecedented sensitivity in the latter. The objective of the current proposal is to validate this technique in humans. To this end we propose the following aims:

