**Specific Aim 1:** Demonstrate BAT mass detection in human subjects. For this aim we will implement hyperpolarized xenon imaging on our clinical scanner and we will compare the images obtained before stimulation of BAT thermogenesis with those obtained during stimulation of BAT thermogenesis. Our working hypothesis is that, during stimulation of BAT thermogenesis the lipophilic gas will accumulate in the highly perfused BAT tissue enabling us to clearly delineate it.

**Specific Aim 2:** Demonstrate detection of BAT thermogenesis in humans. For this aim we will measure BAT temperature by measuring the chemical shift of lipid-dissolved xenon. Our working hypothesis is that, during stimulation of BAT thermogenic activity, changes in BAT temperature would be detected as a shift in the resonance frequency of lipid-dissolved xenon.

By the end of the proposed project we expect to have demonstrated the feasibility of HP xenon

MRI detection of human BAT mass and thermogenic activity. These studies will also provide preliminary data for powering a future clinical trial with which we aim to investigate the incidence and activity of this tissue in the human population.

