**SIGNIFICANCE:** Most of our knowledge on BAT comes from animal studies. In small animals we know that BAT prevents obesity and improves and reverses insulin insensitivity. In humans the role of this tissue is less clear. This is because human BAT studies have been limited mainly to retrospective studies on cancer patients due to lack of safe and reliable detection techniques to study the small quantities of diffusely distributed BAT depots present in humans *in vivo*. Fusion FDG-PET/CT remains the gold-standard imaging modality for non-invasive studies of metabolically active BAT. However, this technique is intrinsically insensitive to BAT metabolism as only small amounts (less than 10%) of glucose are taken up by activated BAT. The rest of the substrate (more than 90%) is made by fatty acids released from intracellular lipid storages. As such, the activity of this tissue is clearly underestimated by FDG-PET scans. This is especially true for overweight and obese subjects, the target population for BAT, in whom the intracellular lipid storage is more abundant (brown fat cells are swollen with fat) than in lean subjects. Therefore, this tissue relies even less on circulating glucose for thermogenesis, further limiting its detectability by FDG-PET scans. More importantly, the elevated risk of ionizing radiation and radionuclide tracer radiation exposure from these scans precludes repetitive BAT screening in healthy and young subjects, scans which are needed to correctly estimate the true prevalence of BAT, to determine the physiological relevance of BAT in humans, and to test the efficacy of new anti-obesity treatments. With this proposal we aim to fulfill this need. HP xenon MRI is extremely sensitive to the more lipid rich and less thermogenically active BAT of obese phenotypes (see comparison with FDG-PET in Fig 1) and, by being non invasive, can be repeatedly used on healthy subjects to track BAT function over time. In addition it allows direct measurement of BAT cell temperature (Fig. 2) and therefore represents the only direct way we have to monitor BAT thermogenic activity.

[figure not shown]

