This feasibility study will allow us to estimate the standard deviation for the increase in signal from xenon dissolved in BAT and for the increase in BAT temperature that will then be used to power future trials to investigate the incident of this tissue in the healthy human population and the association between BMI and BAT thermogenic activity. For these aims we plan on enrolling a total of 24 healthy subjects (12 for aim 1 and 12 for aim 2) with a BMI ranging between 18 and 28. Twelve is the minimum sample size recommended in the absence of prior information on which to base our sample size calculation. With 12 subjects per group we should be able to obtain positive results (with a 95% confidence interval) on at least 9 subjects if the true prevalence of BAT is 90% (expected prevalence), and on at least 3 subjects if the true prevalence of BAT is much smaller and close to 50% (estimated by FDG-PET scans).

By the end of the study we expect to have fully assessed the potential of HP xenon to detect BAT mass and activity and to have developed an imaging protocol that can be used in studies aimed to investigate the prevalence of this tissue in humans, its connection with other metabolic diseases such as diabetes, and to study the response to treatments aimed to counteract obesity by increasing BAT mass and or function.

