#### **-Enriched Xenon gas mixture (\$12,240)**

During the imaging study session the subject will receive two doses of 1L of HP Xenon, spaced 40 minutes apart (40 minutes is the minimum time required to produce a 1L of hyperpolarized xenon gas). For the spectroscopy study the subject will receive a total of 4 0.5L of hyperpolarized xenon every 20 minutes. Funds are therefore requested for 4800L of 1% enriched Xe (quoted at \$5,100 per 2000L cylinder by Linde specialty gas) that will lead to a total of 48L (2L per subject x 12 subjects) of enriched Xenon.

The cost of the non-enriched xenon gas as well as the cost of the other gases needed for the xenon polarizer will be covered in its entirety by the PI funds.

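### A single session with no within-subject error estimate cannot fully assess HP xenon: judge Aim 2 temperature changes against within-session noise, and narrow the closing claim to feasibility

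*Combined protocol and SAP*

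**What the plan says.** - **Closing claim (APPROACH, last paragraph):** "By the end of the study we expect to have fully assessed the potential of HP xenon to detect BAT mass and activity". The same sentence goes on to an imaging protocol for later studies, one use being "to study the response to treatments aimed to counteract obesity by increasing BAT mass and or function".
- **Narrower claim (end of SPECIFIC AIMS):** "we expect to have demonstrated the feasibility of HP xenon" MRI detection of BAT mass and thermogenic activity.
- **Reproducibility (SPECIFIC AIMS):** among three limitations of FDG-PET, the second is "It is not reproducible".
- **Aim 1 (APPROACH, Aim 1):** one xenon image before cooling is compared with one during cooling. The budget section on enriched xenon agrees: "During the imaging study session the subject will receive two doses of 1L of HP Xenon, spaced 40 minutes apart".
- **Aim 2 (APPROACH, Aim 2):** four doses are inhaled, all during cold exposure. The xenon frequency is tracked to follow BAT temperature, and the change is correlated with BMI. Changes below 2 °C are expected, and changes as small as 0.2 °C are said to be detectable.
- **Planned variability (APPROACH, sample-size paragraph):** the SD of the signal increase and the SD of the temperature increase. These are to power later trials of how common BAT is and of its association with BMI.
- **Sessions (Other Direct Costs):** one imaging session of about 2 hours is described per subject.

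No second visit, repeat image under an unchanged condition, within-subject SD, intraclass correlation or repeatability coefficient appears anywhere.

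**The concern.** The plan faults the current standard as not reproducible and then expects its own method to be fully assessed for detection. Detecting thermogenesis in a given person means showing that the measured change exceeds what the measurement would show by chance. With a single change per subject, an SD across subjects cannot separate real differences between people from error in each measurement.

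This bears most on Aim 2. The 0.2 °C detection limit is argued from the temperature sensitivity of the xenon line and its narrow width, with supporting data from mice. No planned analysis checks it in humans, although the readings that could do so will be collected. Without that check, a change of a few tenths of a degree cannot be classed as warming or as scatter, and the correlation with BMI would be run on changes of unknown reliability.

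**Working it through.** **1. Number of sessions.** Inputs from the budget: $19,968 for scan time, $416 per hour, 24 subjects.
- 19,968 / 416 = 48 h, and 48 / 24 = 2 h each, which is one session.
- The budget table gives $1,440 for volunteers; at $60 each, 1,440 / 60 = 24 payments.
- The budget also conflicts with itself. The scan-time formula of 3 hours and 10 subjects gives 416 × 3 × 10 = $12,480. The compensation heading of $1,920 gives 1,920 / 60 = 32 payments.
- The table total fits 24 payments: 8,640 + 19,968 + 12,240 + 1,440 = 42,288.

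One session per subject is therefore the best reading, but no sentence states it outright.

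**2. Degrees of freedom for within-subject error.**
- Aim 1: one image per condition per subject leaves 0 df for test-retest error.
- Planned SD of the increase: one change per subject in 12 subjects gives 11 df, but its variance is the between-subject variance of true change plus the error variance. The two cannot be separated.
- Aim 2: with one reading per dose and a straight line fitted for each subject, residual df = n × (4 − 2). The documents do not say how many spectra each breath-hold yields, so one reading per dose is an assumption.

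**3. How many subjects may be usable.** The sample-size paragraph expects at least 9 of 12 positive at 90% prevalence and at least 3 of 12 at 50%. Exact binomial tails reproduce both:
- P(X ≥ 9 | 12, 0.9) = 0.974 and P(X ≥ 10) = 0.889.
- P(X ≥ 3 | 12, 0.5) = 0.981 and P(X ≥ 4) = 0.927.

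So 9 and 3 are the largest counts reached with at least 95% probability. They serve here as plausible numbers of subjects with usable BAT spectra.

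**4. Precision of the pooled within-subject SD.** The 95% limits, as multiples of the estimate, are √(df / χ²₀.₉₇₅) and √(df / χ²₀.₀₂₅).

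| Usable subjects | df | Lower | Upper |
|---|---|---|---|
| 12 | 24 | 0.78 | 1.39 |
| 9 | 18 | 0.76 | 1.48 |
| 3 | 6 | 0.64 | 2.20 |

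**5. What the 0.2 °C claim requires.** Take a change as the difference of two readings with independent errors of SD s. Its 95% repeatability limit is 1.96 × √2 × s = 2.77 s.
- For a limit of 0.2 °C, s = 0.2 / 2.77 = 0.072 °C.
- For a limit of 2 °C, s = 2 / 2.77 = 0.72 °C.

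The documents give no human value of s. If the estimated limit came out at exactly 0.2 °C, its 95% range would be 0.16 to 0.28 °C with 24 df, 0.15 to 0.30 °C with 18 df and 0.13 to 0.44 °C with 6 df (0.2 times the multipliers above).

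**The case against.** The strongest reply is that this is a Phase 1 feasibility study. SPECIFIC AIMS says so, the sample-size paragraph opens that way, and test-retest work normally follows first detection in humans. That stands: nothing here requires a repeat visit, and the aims do not promise to show that HP xenon is reproducible.

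Three stronger readings are tempting, and the documents do not support them.

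- **That the method is said to be fully assessed for treatment response.** In the closing sentence those words govern detection of BAT mass and activity. Treatment response is only a later use of the imaging protocol.
- **That SIGNIFICANCE claims demonstrated repeatability.** The words "can be repeatedly used on healthy subjects to track BAT function over time" depend on the method being non-invasive and follow a passage on radiation exposure. They concern safe repeat use.
- **That the SDs would be used to size longitudinal trials.** The sample-size paragraph reserves them for trials of how common BAT is and of its association with BMI. For such cross-sectional questions, an SD containing both between-subject variation and measurement error is the relevant one.

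The Aim 2 readings are also imperfect replicates, because temperature is expected to move during cooling. A straight line leaves any curvature in the residual, which inflates the SD. It also absorbs linear instrument drift, which cannot then be told apart from warming. These points limit what the SD means, but it is still more informative than having no error figure.

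**Conclusion.** The point holds in limited form. The closing claim exceeds a design with one session per subject, no repeated Aim 1 condition and no planned within-subject error estimate. The planned SDs are fit for their stated purpose, but they cannot show whether an individual temperature change exceeds measurement noise, and the 0.2 °C figure is not tested in humans.

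The gap can be partly closed from the planned data. The error SD would be known to within about 0.78 to 1.39 times its estimate at best, and 0.64 to 2.20 times if only 3 subjects give usable spectra. This assumes one usable reading at every dose, a roughly linear course and independent, normal errors. Because curvature adds to it, the figure leans high as an estimate of random scatter.

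The analysis says nothing about between-day repeatability or about Aim 1. A reader might infer that HP xenon is as irreproducible as FDG-PET is said to be. The documents give no evidence either way.

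**What to change.** 1. **APPROACH, Aim 2.** Add a pooled within-session, within-subject SD of the temperature readings around each subject's own linear trend, with its 95% limits, df and number of usable readings. Report it beside the between-subject SD. Compare the observed changes and the 0.2 °C claim with the repeatability limit of 2.77 times that SD. Use one value per dose, and note that curvature inflates the SD and that linear drift is not captured. The volume per Aim 2 dose differs between APPROACH (1 L) and the budget (0.5 L). The two passages must be reconciled so that it is clear what each reading represents.
2. **APPROACH, closing paragraph.** Replace the claim of full assessment with *assessed feasibility in a single session*, in line with SPECIFIC AIMS. State that between-day repeatability and Aim 1 repeatability are not assessed.

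The cost is one short analysis of readings already planned and a few words. No extra visit, scan or dose is needed. The stated conclusion becomes more modest.

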#### **A. Proposed involvement of human subjects**

All research involving human subjects will be carried out at the University of North Carolina at Chapel Hill. All MRI experiments will take place in the Biomedical Research Imaging Center, where the PI's lab for hyperpolarized  $^{129}\text{Xe}$  gas MRI and the 3T Siemens MRI scanner is located. A medical technician, with knowledge and skills consistent with those provided in the American Heart Association's Advanced Cardiac Life Support training will observe the subjects whenever they are breathing xenon gas. Supplemental oxygen (adjusted to flow at 4 liters/minute), suction source, bag valve mask, ventilation device and an airway support device will be available in the MR scanner room. During scanning, a MRI compatible pulse oximeter will be used to monitor the subject's heart rate and blood oxygenation.

A total of 24 healthy subjects, without any metabolic disease, of ages 18 to 40 will be recruited to participate. All subjects will undergo hyperpolarized xenon-129 MR. Healthy subjects are considered those who have never been diagnosed with metabolic diseases, and have no history of any chronic lung disease such as asthma, COPD, or CF.

Since our aim is devoted to test the efficacy of the new methodology for the detection of BAT, there is no justification to scan children under 18 years old. Pregnant or lactating women will be excluded due to potential health risks. All subjects must be able to undergo an MRI examination (e.g., no MRI incompatible implanted devices or other MR contra-indications).

[name] will be present during all hyperpolarized xenon-129 MR scans.

#### Practice xenon inhalation for subjects before placement into the MR scanner:

Individual subject sensitivity to xenon inhalation will be practiced before MR imaging. The subject will be directed to breathe 1-L of undiluted xenon (natural isotopic abundance) and to hold his breath for 15-20s. Oxygen saturation, heart rate, and blood pressure will be continuously recorded. If the effects of xenon inhalation are deemed intolerable by the subject the amount of xenon will be lowered. If the blood oxygen saturation drops significantly (5%) below the subject's baseline and/or the pulse rate rises by 40 bpm, the practice session will be interrupted to explore the cause. If the cause cannot be identified and rectified, the subject will be excluded from the study.

#### Hyperpolarized xenon-129 MRI:

Subjects will be positioned supine within the MR scanner. The dual tuned xenon/proton surface coil will be positioned above the supraclavicular area. After breathing normally for a few minutes, the subject will exhale completely to residual volume, and then inhale a 1-L volume of undiluted hyperpolarized xenon-129, followed by a breath-hold lasting from 10-15 s during and after which imaging will be performed. The subject will then exhale fully and breathe normal air. Xenon doses will be administered no less than 15 minutes apart. During the MRI exam, oxygen saturation, heart rate, and blood pressure will be continuously recorded. These parameters, along with respiratory rate and subjective symptoms, will also be assessed after each dose. Immediately after inhalation, the subject will also be asked to report any symptoms or effects from xenon.

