Dynamic spectroscopy data have shown the possibility to track BAT temperature over time by measurement of the chemical shift of lipid-dissolved xenon. We demonstrated for the first time MR thermometry by hyperpolarized xenon gas. This method is based on the temperature dependence of the chemical shift of lipid dissolved xenon, which we measured for the first time *in vivo* to be  $-0.2 \text{ ppm}^{\circ}\text{C}$ , (Fig 2.a), i.e. 20 times larger than that of water protons currently used for MR thermometry in lean tissues. This higher sensitivity of lipid-dissolved xenon to temperature, coupled with the lower gyromagnetic ratio of xenon (which makes xenon less sensitive to possible magnetic field in homogeneities present in fatty tissues), allowed us to detect BAT thermogenic activity in mice (Fig.2.b). To this end we will acquire dynamic spectroscopy data from xenon dissolved in BAT during stimulation of BAT thermogenesis by mild cold exposure. During these scans we will track the resonance frequency of lipid-dissolved xenon to detect changes in BAT temperature during thermogenic activity. Although in humans we expect temperature changes less than  $2^{\circ}\text{C}$ , the high sensitivity of xenon to temperature and the narrow line width can allow us to detect changes as small as  $0.2^{\circ}\text{C}$ .

**Fig.2** a) Linear temperature shift of the lipi-dissolved xenon frequency as acquired *in vivo* in an obese mouse. b. Thermogenic activity as detected by hyperpolarized xenon gas. The graph shows the resonance frequency shift of lipid-dissolved xenon and the corresponding shift in BAT temperature right after injection of NE.

For these studies the subject will inhale 4 doses of 1L each of xenon during mild cold exposure, achieved with a water cooling blanket. After inhalation, the subject will be asked to hold his breath for 15-20 seconds, during which we will trigger the acquisition of xenon spectra. The spectra will then be fitted with homemade Matlab routines to extract lipid-dissolved xenon resonance frequency that will be used to detect any change in BAT temperature.

The change in BAT temperature will then be analyzed as function of BMI to establish whether or not there is an association between BMI and BAT temperature increase (Pearson correlation and Spearman correlation coefficient calculation).

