#### B2. Risks of xenon inhalation:

Xenon is a general anesthetic when breathed continuously for long periods of time (minutes) at concentrations greater than 50% (anesthetic dose ~70%). There is also the theoretical risk that HP 129Xe, if given in sufficiently large volumes in forms that do not include oxygen, could cause or exacerbate hypoxia in a subject. However, a recent clinical trial performed at Duke University, where the same protocol was used to image lung ventilation function, has not caused hypoxia but only mild, transient, xenon-related symptoms, consistent with its known anesthetic properties, such as dizziness, paresthesia, euphoria, and hypoesthesia that have resolved soon after discontinuing gas administration(1).

B3. Purity of laser polarized xenon:

The purity of the laser polarized gases is very high because:

1. The initial source of xenon has a purity of at least 99.99%;
2. Only nitrogen is added to the gas before laser polarization;
3. Only room air and oxygen are added to the gas after laser polarization;
4. All chambers into which the gases are transferred are always pumped to a vacuum before gas is transferred into them; and
5. The rubidium vapor used during the polarization process is removed by allowing the polarized gas to pass through either a Teflon filter or a cold trap.

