**C2. Xenon Inhalation:**

The xenon dosing strategy is designed to minimize the previously described xenon physiological effects from the inhalation. In addition, a licensed medical professional will observe the subject whenever they are breathing xenon, and MR compatible monitoring equipment and supplemental oxygen and other equipment for artificial ventilation will be available. In addition, there will be practice sessions to assess the subject's response to the gas mixture. If there is any significant discomfort by a subject, he/she will be excluded from the project.

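### Symptoms and respiratory rate are checked after each xenon dose with no pre-dose check described, and 60 of 72 scanner doses fall during cooling, so xenon effects may not be separable from other effects

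*Combined protocol and SAP*

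**What the plan says.** Monitoring in the scanner is set out in section A under the heading Hyperpolarized xenon-129 MRI. Three vital signs are recorded continuously. The plan then adds: "These parameters, along with respiratory rate and subjective symptoms, will also be assessed after each dose". Right after the breath, the subject is also asked about anything felt from the gas. In the text supplied, no symptom or respiratory-rate check is placed before a dose, before cooling, or during cooling without xenon.

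Cooling comes from a water blanket at about 15 °C on the lower abdomen and upper legs (Approach, Aim 1). In Aim 1, "we will compare the images obtained before stimulation of BAT thermogenesis with those obtained during stimulation of BAT thermogenesis". In Aim 2, "the subject will inhale 4 doses of 1L each of xenon during mild cold exposure".

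Section B2 describes xenon symptoms seen in a cited lung-imaging study, "such as dizziness, paresthesia, euphoria, and hypoesthesia that have resolved soon after discontinuing gas administration". It introduces that study as one "where the same protocol was used to image lung ventilation function". Section B contains no item on cooling.

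Before entering the scanner, every subject takes one practice dose, with no cooling described. Section C2 mentions these practice sessions and then states: "If there is any significant discomfort by a subject, he/she will be excluded from the project".

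**The concern.** This is a Phase 1 study under an IND, and it chooses to collect symptoms after every dose. To read such an observation as a response to the dose, one needs to know whether the symptom was there just before it. Continuous recording supplies that reference for saturation, heart rate and blood pressure. Nothing described supplies it for symptoms or respiratory rate.

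The gap matters more here because most scanner doses coincide with a second intervention. Two of the four symptoms that B2 names for xenon, paresthesia and hypoesthesia, are sensations that skin cooling might plausibly produce by itself. The cited study does not settle the matter: B2 mentions no cooling in it, whereas this protocol adds cooling. At stake is whether the symptom and respiratory-rate data can be interpreted at all for cooled doses, above all in Aim 2.

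**Working it through.** **Inputs**
- Subjects: "24 healthy subjects (12 for aim 1 and 12 for aim 2" (Approach, sample-size paragraph).
- Aim 1 scanner doses: "the subject will receive two doses of 1L of HP Xenon, spaced 40 minutes apart" (budget, Enriched Xenon gas mixture). One is before and one during cooling (Specific Aim 1; Approach, Aim 1).
- Aim 2 scanner doses: four per subject, all during cooling (Approach, Aim 2). The budget also gives four.
- Practice doses: one per subject, before the scanner (section A, practice inhalation).

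**Check against the plan's own total.** The plan states no total number of doses. The only stated total that depends on the schedule is the 48 L of enriched xenon in the budget. With the budget's volumes, 12 × 2 × 1 L + 12 × 4 × 0.5 L = 24 + 24 = 48 L, so the dose counts reproduce it.

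Two inconsistencies appear in passing and need reconciling. The Approach gives 1 L per Aim 2 dose, which would make 12 × 2 + 12 × 4 = 72 L. The budget's bracket of 2 L × 12 subjects makes 24 L, not 48 L. Neither affects the count below, because both sources give four Aim 2 doses.

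**Dose count**

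| | Uncooled | Cooled | Total |
|---|---|---|---|
| Aim 1 scanner | 12 × 1 = 12 | 12 × 1 = 12 | 24 |
| Aim 2 scanner | 0 | 12 × 4 = 48 | 48 |
| All scanner | 12 | 60 | 72 |
| Practice | 24 | 0 | 24 |
| All xenon | 36 | 60 | 96 |

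Cooled share of scanner doses: 60/72 = 83.3%. Cooled share of all xenon doses: 60/96 = 62.5%.

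**What the uncooled doses can show**
1. The 12 uncooled Aim 1 doses always come first, so within a subject cooling is confounded with dose order.
2. Aim 2 subjects have no uncooled scanner dose. Their only uncooled xenon is the practice breath, taken outside the scanner, and no structured symptom record is described for it.
3. All 36 uncooled doses are observations of xenon without cold. To tell whether a symptom at a cooled dose was already present, one needs the same subject, under cooling, before the breath. None of the 96 doses comes with that observation.

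**The case against.** The strongest case against runs as follows. The aims are BAT mass and BAT temperature. No tolerability endpoint, symptom rate or causality analysis is defined, so no planned estimate is biased. The post-dose checks are bedside monitoring. No pre-dose check is stated, but that is silence, not a prohibition. Every subject has an uncooled practice dose meant to gauge individual sensitivity to xenon. The symptoms are described as transient, and the question is put right after the breath, which helps to tie an event to the dose. Finally, nothing in the documents says that mild cooling causes tingling or numbness.

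Most of this stands, and it limits the point. Three stronger readings that a reader might infer are not supported:
- **Cold symptoms are recorded as xenon effects.** No attribution rule is written. Symptoms are assessed generally after each dose, in addition to the question about the gas. Attribution is left open, not fixed wrongly.
- **The xenon symptom rate is biased upward.** No such rate is planned, and any figure for its inflation would rest entirely on assumed rates.
- **Misattribution can cost a subject.** The C2 discomfort sentence directly follows the one on practice sessions, which involve no cooling. Read more broadly, it is indifferent to cause, so the label on the symptom would not change the outcome.

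What the objection does not remove is the missing comparison. Practice doses and prompt questioning help to recognise a xenon effect. Neither shows what the subject felt under cooling before the breath.

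**Conclusion.** The point holds as a limitation on interpretability with a cheap remedy. The plan describes post-dose checks of symptoms and respiratory rate and no pre-dose or cooling-only check. Cooling accompanies 60 of 72 scanner doses (83.3%), or 60 of 96 xenon doses with practice included (62.5%), and every Aim 2 scanner dose. Symptoms noted after those doses may not be separable from effects of cold or of the scanner setting.

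The conclusion rests on two things: that silence about a pre-dose check means none is planned, and that cooling can produce sensations overlapping with those listed for xenon. The second is an assumption from outside the documents. Even without it, a check before the dose is the better method, since position, anxiety or an earlier dose could also account for a symptom.

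A separate matter needs clarifying. In the practice section, effects the subject finds intolerable lead to a smaller amount of xenon, and exclusion follows unexplained saturation or pulse changes. C2 instead excludes for significant discomfort and names neither session nor cause. These passages must be reconciled.

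**What to change.** Under Hyperpolarized xenon-129 MRI, amend the sentence on post-dose assessment so that symptoms and respiratory rate are assessed immediately before and after each dose. Use the same symptom list both times, in the same thermal state. Tabulate symptoms that are new or worse after the dose separately from those already present before it. Do not label the latter as cooling effects: they could equally come from position, anxiety or a previous xenon dose, and a default label would replace one unsupported attribution with another.

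The cost is about one minute per dose and one more line on the record form. That is 2 minutes per Aim 1 subject, 4 per Aim 2 subject, and 72 × 1 = 72 minutes over the study. It fits in the few minutes of normal breathing already planned before each inhalation and needs no extra dose, staff or equipment.

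Separately, the sponsor should reconcile the practice-inhalation section with C2, stating which session and which events the discomfort exclusion covers.
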